### **SECONDARY OUTCOMES:**

- ***Preeclampsia:*** characterized by hypertension and proteinuria occurring after the 20th week of pregnancy. Hypertension is a blood pressure of 140/90 mm Hg or above. In severe pre-eclampsia the diastolic blood pressure is usually 110 mm Hg or above and there may also be one or more of the following symptoms: severe headache, blurred vision, nausea and/or vomiting, abdominal pain and a diminished urinary output, i.e., oliguria. ***Early onset Preeclampsia*** develops before 34 weeks of gestation.
- ***Eclampsia:*** Very serious complication of pregnancy characterized by convulsions and coma. It may be preceded by signs of pre-eclampsia or the onset may be rapid and sudden. Eclamptic fits can occur in pregnancy, labour or soon after delivery.
- ***Small for gestational age:*** newborns with weights below the 10th percentile for gestational age.
- ***Perinatal mortality:*** The number of stillbirths and deaths in the first week of life per 1,000 live births, the perinatal period commences at 22 completed weeks (154 days) of gestation and ends seven completed days after birth.

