#### **3.2 Secondary Hypotheses and Associated Outcomes**

The study will also test three secondary hypotheses:

- Infants of women who take antenatal daily LDA initiated at 6 0/7 to 13 6/7 weeks GA will be at lower risk of being small for gestational age (SGA).
- Women who take antenatal daily LDA initiated at 6 0/7 to 13 6/7 weeks GA will have lower risk of: eclampsia and preeclampsia. Note that this hypothesis will be operationalized as evidence of hypertensive disorders of pregnancy as defined in more detail in Sections 9 and 12.
- Infants of women who take antenatal daily LDA initiated at 6 0/7 to 13 6/7 weeks GA will be at lower risk of perinatal mortality.

These secondary hypotheses will be tested using the following outcomes.

- Small for gestational age infants include newborns with weights below the 10th percentile for gestational age, as defined by Intergrowth Standards.
- Risk of Pregnancy Induced Hypertension (eclampsia and/or preeclampsia) defined as a binary outcome of any of new onset hypertension that occurs beyond 20 weeks gestational age, preeclampsia, or eclampsia happening between initiation of study dosing and participant completion of the study at 6 weeks after delivery. Eclampsia is a serious complication of pregnancy characterized by convulsions and coma. It may be preceded by signs of pre-eclampsia or the onset may be rapid and sudden and can occur in pregnancy, labor or soon after delivery. Preeclampsia is characterized by hypertension and proteinuria occurring after the 20th week of pregnancy. See Sections 9 and 12 for more detail.

- Perinatal mortality is a binary outcome that includes any stillbirth occurring after 20 weeks pregnancy and any early neonatal death that occurs within 7 days after delivery.

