### Modified Intention to Treat (mITT) Population

**The primary analysis population will be the modified intention to treat population**, which includes all eligible, randomized participants who provide any post-baseline outcome data and who deliver at 20 weeks gestational age or greater. All participants will be assigned to the arm to which they were randomized irrespective of treatment received. Unless specified otherwise, data for this population will be analyzed as available (i.e. irrespective of protocol deviation occurrence, subsequent study participation termination, or study drug withdrawal). This population will also be used for many of the secondary analyses. Note that this population represents a change from the protocol, which indicates that the ITT population will be used for the primary analyses. This change was made prior to any unmasking.

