Small for Gestational Age	Binary	
The unit of analysis is the infant delivered from each individual pregnancy. The outcome will be classified as “Yes” if the infant is classified as SGA, defined as a newborn with weight below the 10th percentile for gestational age” and “No” otherwise. Note that growth curves appropriate for each GN site based on Intergrowth standards will be used to define the expected gestational age distribution.
 
For any outcomes involving birth weight, the reported weight will only be used to calculate that outcome if collected within 4 days of birth. Any weight captured after 4 days will be excluded.
 
Analysis Population: mITT

Perinatal Mortality	Binary	
The unit of analysis is the infant delivered from each individual pregnancy. The outcome will be classified as “Yes” if the infant is a fresh or macerated stillbirth or a death in the first week of life; the perinatal period commences at 20 completed weeks (154 days) of gestation and ends seven completed days after birth. Pregnancies terminated prior to 20 completed weeks of gestation will be treated as missing for this outcome.
 
Analysis Population: mITT

Variable	Type	Definition
Other Outcomes of Interest—Maternal Outcomes		
Preterm, preeclampsia	Binary	
The unit of analysis is the woman randomized to the trial who delivers after 20 weeks gestational age. The outcome will be defined as delivered at less than 34 weeks GA AND also meeting the criteria for the endpoint “Preeclampsia and eclampsia (or more appropriately hypertensive disorders of pregnancy).”
 
Analysis population: mITT

Vaginal Bleeding	Binary	
The unit of analysis will be individual woman. Per the protocol, Vaginal Bleeding is defined as: “Bleeding during pregnancy (i.e., WHO generally defines as ‘light’ or ‘heavy’ bleeding based on clinical symptoms).” This outcome will be defined based on Question 2e of Form ASP06 and will be classified as “Yes” if the response to this question is Yes at any bi-weekly visit, and No if all completed biweekly visits have either a No or a DK response. Any woman with at least one biweekly visit form will be included in the denominator; the outcome will be classified as missing if a subject has no biweekly visit forms.
 
Analysis population: ITT

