Fetal Loss	Binary	
The unit of analysis will be the individual delivered fetus or infant and per the protocol, the event of fetal loss is defined as: "Spontaneous loss <math>\geq</math> 16 weeks GA plus perinatal mortality." This binary outcome measure will be defined in the analysis data set based on gestational age as measured via the ASP forms and mortality outcomes as determined from Forms MN02 and MN03 from the MNH Registry. Any death of an infant greater than 16 weeks GA and prior to 7 days post-delivery will be classified as "Yes" and live births classified as alive at 7 days will be classified as "No." Any fetal loss (including MTP or miscarriage) that occurs prior to 16 weeks will be treated as a missing value.
 
Analysis population: ITT

Variable	Type	Definition
Spontaneous abortion	Binary	
The unit of analysis is the individual pregnancy. Per the protocol, the binary outcome of spontaneous abortion is defined as: "Premature expulsion of a non-viable fetus from the uterus at < 20 weeks gestation." This outcome will be defined based on Questions A7-4 or C1 from Form MN02 from the MNH registry and will be classified as "Yes" if the response to A7-4 is listed as the Mode of Delivery or the response to C1. Fetal/Neonatal outcome is answered 1. Miscarriage and "No" otherwise. Per the MNH Registry Manual of Operations, that mode of delivery should be used if "A delivery prior to 20 weeks gestation (or <500 g). Miscarriage is also known as spontaneous abortion."
 
Analysis population: ITT

Stillbirth	Binary	
The unit of analysis will be the individual infant that delivers at 20 weeks gestational age or greater during the specified analysis period. The event will be classified as "Yes" if the infant is classified as a non-macerated still birth or with maceration status unknown via Forms MN02 and MN05 in the MNH Registry and "No" if the baby is born alive as specified via Form MN02 in the MNH Registry. Note that infants classified as Macerated still births are not included in this population. Also note that deliveries classified as miscarriages but that have GA of 20 weeks or greater will be reclassified as stillbirths.
 
Analysis population: mITT

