## **12. CHANGES TO THE ANALYSES PLANNED IN THE PROTOCOL**

Additional sensitivity analyses beyond those included in the original protocol have been included in Sections 7.3 and 9 to account for loss-to-follow-up and to account for early pregnancy losses. Also, one secondary outcome variable has been modified and one secondary outcome variable has been added. The outcome of risk of preeclampsia or eclampsia has been modified to clarify that this outcome is the risk of a hypertensive disorder of pregnancy. This modification was made to clarify the true variable of interest, reflecting the data collection process used in the MNH registry. The outcome of preterm, preeclampsia has been added to the secondary outcome list to reflect additional research that was reported on this outcome after the study was launched.

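### SAP 9.2 starts the perinatal period at 20 weeks but gives the day count for 22 weeks, and the move from the protocol's 22 weeks is not declared in SAP 12

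*Combined protocol and SAP*

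**What the plan says.** Start of the perinatal period:

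- Protocol Appendix 3, secondary outcomes: "the perinatal period commences at 22 completed weeks (154 days) of gestation and ends seven completed days after birth".
- SAP 9.2, Perinatal Mortality row: "the perinatal period commences at 20 completed weeks (154 days) of gestation and ends seven completed days after birth". Apart from the number of weeks, the two statements are identical.
- SAP 3.2 gives no day count. It counts "any stillbirth occurring after 20 weeks pregnancy and any early neonatal death that occurs within 7 days after delivery".

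Other SAP rules that fix which deliveries enter the outcome:

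- SAP 9.2, same row: "Pregnancies terminated prior to 20 completed weeks of gestation will be treated as missing for this outcome".
- SAP 5, the mITT population, which is the population for this outcome: participants "who deliver at 20 weeks gestational age or greater".
- SAP 9.2, Stillbirth row: "deliveries classified as miscarriages but that have GA of 20 weeks or greater will be reclassified as stillbirths". The Late Abortion row has a similar rule.

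Declared changes: SAP 12 says that "one secondary outcome variable has been modified and one secondary outcome variable has been added". It names the modified one as preeclampsia/eclampsia (now hypertensive disorders of pregnancy) and the added one as preterm preeclampsia. Perinatal mortality is not mentioned.

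**The concern.** A gestational-age threshold given in weeks and in days should be the same threshold twice. Here the two halves are different cut-offs, and the day count is the protocol's own valid one. It therefore does not look like obvious nonsense to someone coding from the row. The SAP also keeps a 22-week start elsewhere, for antepartum hemorrhage in 9.2.

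Two things are at stake. The first is whether a stillbirth or early death at 20w0d to 21w6d is counted as an event in a named secondary outcome. The second is disclosure. The protocol and the SAP define the same outcome from different starting points, and the SAP section meant to record such differences is silent. Protocol version 1.3 revised the outcome lists, yet Appendix 3 still reads 22 weeks, so the disagreement stands in the current texts.

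**Working it through.** **1. Conversion.** Days = completed weeks × 7.

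- Protocol Appendix 3: 22 × 7 = 154. The protocol's figure reproduces.
- SAP 9.2: 20 × 7 = 140, not 154. In reverse, 154 / 7 = 22.0 weeks.
- Gap: 154 − 140 = 14 days, that is days 140 to 153, or 20w0d to 21w6d.

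**2. Which half of the SAP phrase is wrong.** Take a stillbirth at 21w0d, which is 21 × 7 = 147 days, and apply each rule.

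| Rule | Treatment at day 147 |
|---|---|
| SAP 3.2, stillbirth after 20 weeks | event |
| SAP 5, mITT threshold of 20 weeks | in the analysis population |
| SAP 9.2, missing only before 20 completed weeks | not missing |
| SAP 9.2, miscarriage entries at 20 weeks or more | become stillbirths |
| SAP 9.2, perinatal period, week count | inside |
| SAP 9.2, perinatal period, day count | outside (147 < 154) |
| Protocol Appendix 3 | outside (147 < 154) |

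Every SAP rule except the day count agrees on 20 weeks. The day count agrees only with the protocol. That it was carried over from the protocol sentence is an inference, but a natural one.

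**3. Effect of coding the day count literally.** With a start of 154 days or more, deliveries on days 140 to 153 remain in the mITT and are not set to missing, yet lie outside the perinatal period. No SAP rule assigns them a value on that reading, and they could end up coded as non-events.

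**4. Declaration.** SAP 12 counts one modified secondary outcome. The change from 22 to 20 weeks is a second, so the count is one short on the documents' own texts. The SAP does flag departures elsewhere: the row in 9.2 for preterm birth before 34 weeks says that it departs from the protocol, and Section 5 records a population change and places it before unmasking. The perinatal row has no such note.

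**5. Is power affected?** SAP 6.2 assumes 45 perinatal deaths per 1,000 and 5,483 evaluable per arm. The two-sided 5% normal approximation is

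z = [d − 1.96 √(2p̄(1 − p̄)/n)] / √([p₁(1 − p₁) + p₂(1 − p₂)]/n), with d = p₁ − p₂ and p̄ the mean of p₁ and p₂.

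- 24% reduction: p₂ = 0.045 × 0.76 = 0.0342 and d = 0.0108. Then z = (0.0108 − 1.96 × 0.003725) / 0.003723 = 0.94, so power is 82.6% (stated 80%).
- 27% reduction: p₂ = 0.045 × 0.73 = 0.03285, and power is 90.8% (stated 90%).
- As an assumption only: if the wider window raised the rate to 47 to 50 per 1,000, power for a 24% reduction would be 84.3% to 86.5%.

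The stated power is met at the plan's own rate, and the point does not turn on it.

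**The case against.** The strongest reply is that the intent is plain. Five places in the SAP point to 20 weeks, including the sentence that follows directly in the same row, so this is one stale parenthesis. Protocol 3.1.2 already analyses this outcome in pregnancies delivering after 20 weeks, so a 20-week threshold is not foreign to the protocol. SAP 7.5 treats secondary analyses as exploratory with descriptive p-values. Either cut-off applies equally to both arms, and SAP 4.4 puts unmasking after data lock.

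Most of this stands. It settles which number to correct and lowers the weight of the slip. It does not remove the need to correct an operative definition, and it does not answer the missing entry in SAP 12, which is the stronger half of the point.

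Three stronger readings are tempting, and the documents do not support them:

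- A reader might infer that the SAP leaves open whether deaths at 20w0d to 21w6d count. Read as a whole, it does not: 20 weeks is intended.
- A reader might try to size the effect as a share of the roughly 247 deaths per arm implied by 0.045 × 5,483 = 246.7. The documents give no share for the 14-day window. They also do not say which gestational-age start lies behind the 45 per 1,000, so even the direction of any shift in that rate is unknown.
- A reader might infer that the outcome was changed quietly in the light of results. SAP 3.2 states the 20-week definition openly, and nothing in the documents suggests knowledge of results by arm. What is missing is a record of when the change was made.

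**Conclusion.** The point holds in two parts. First, the day count in the SAP 9.2 perinatal mortality row is wrong by 14 days: it should be 140 if 20 weeks is intended, as the rest of the SAP shows. This is a minor slip, but it sits in the operative definition of a named secondary outcome. Second, the SAP moves the start of the perinatal period from the protocol's 22 weeks to 20 weeks without declaring it, either in SAP 12 or in the row itself.

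The arithmetic needs no assumption. That 20 weeks is the intended start is a reading of SAP 3.2, 5 and 9.2 together. No number of deaths, shift in rate or bias between arms is claimed.

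**What to change.** - In the SAP 9.2 perinatal mortality row, write 20 completed weeks (140 days). This agrees with SAP 3.2, the mITT threshold and the missing-data sentence in the same row.
- In SAP 12, add perinatal mortality to the modified secondary outcomes: start changed from the protocol's 22 weeks (154 days) to 20 weeks (140 days), with the date of the change and whether the study was still masked. Correct the count of modified outcomes to match.
- Optionally, report the protocol's 22-week version as a sensitivity row beside the main result, so that readers can see whether the cut-off matters.

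The cost is two short text edits and, if the option is taken, one extra table row. No new data are needed, because gestational age at delivery is already required for the primary outcome.

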### **3.5 STUDY MONITORING PLAN**

#### **3.5.1 Reporting Serious Adverse Events**

Serious Adverse events (SAEs) will be monitored continuously using a special form that will be required for any event that meets the following criteria:

- Results in death;
- Is life-threatening;
- Requires hospitalization or prolongs existing hospitalization;
- Results in persistent or significant disability or incapacity;
- Any other serious or unexpected adverse event that the study investigator(s) feels should be reported.

The specific adverse events to be monitored in this trial include maternal death, upper GI bleeding (vomiting blood), fetal anomaly, gastroschisis, post-partum hemorrhage, or antepartum hemorrhage. The occurrence of any of these events will also trigger completion of the Serious Adverse Events Form.

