Preeclampsia and eclampsia (or more appropriately hypertensive disorders of pregnancy)	Binary	
The unit of analysis is the woman randomized to the trial, but the outcome will be defined by the characterization of evidence of hypertensive disorder, including either preeclampsia or eclampsia occurring during the pregnancy. The algorithm for defining this endpoint is included as an addendum to this SAP in HypertensionAlgorithm_V1.1_10052018 (amendments to this algorithm may occur as part of the endpoint adjudication process and will be documented in new versions of this addendum accordingly).
 
 
• Briefly, any of the following will count as evidence of hypertensive disease: 
 
○ Any reported SAE of preeclampsia or eclampsia.
 
○ M NH registry report of hypertensive disease, preeclampsia or eclampsia.
 
○ Reports of elevated blood pressures that meet criteria based on the ACOG 2013 “Hypertension in Pregnancy” Task Force Report at any point after 20 weeks GA. 
 
▪ The only case that will programmatically qualify for evidence of hypertension is: Any individual with 2 consecutive timepoints with <math>\geq 140</math> mm Hg systolic or <math>\geq 90</math> mm Hg diastolic where those timepoints occur more than a week (7 days) apart. The criteria (e.g. elevated systolic or elevated diastolic) must be consistent for the two consecutive visits.
 
 
 
 
 
• For individuals that do meet the above criteria 
 
○ If they have less no reports of elevated blood pressure or a single report of elevated blood pressure that is followed by a normal value, they will not be considered to have evidence of hypertensive disease.
 
○ If they have any other reports of elevated blood pressure, their outcome classification will be adjudicated in a masked manner by clinical experts.
 
 
 
 
Will exclude any MTP but include withdrawals and terminations as data are available. Analysis Population: mITT
 
.

Variable	Type	Definition

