Antepartum Hemorrhage	Binary	
The unit of analysis will be individual woman with a delivery after 22 weeks. Per the protocol, antepartum hemorrhage is defined as: “Bleeding from the genital tract at any time after the 22nd week of pregnancy and before the birth of the baby. There are two main causes of antepartum hemorrhage, placenta previa and abruptio placentae.” This outcome will be defined based on Question A8b from Form MN02 from the MNH Registry. The event is defined as follows in the MNH Registry Manual of Operations: “Defined as blood loss of > 1000 cc of blood prior to delivery.”
 
Analysis population: mITT

Variable	Type	Definition
Postpartum Hemorrhage	Binary	
The unit of analysis will be individual woman. Per the protocol, postpartum hemorrhage is defined as: "Blood loss of 1000 ml or more from the genital tract after delivery and up to six weeks post-delivery. Common causes include atony (poor muscle tone) of the uterus or trauma to the genital tract, e.g. tears of the vagina, cervix, or lower segment of the uterus." This outcome will be defined based on Question A8c from Form MN02 or Question B7 from Form MN03 from the MNH Registry. The event is defined as follows in the MNH Registry Manual of Operations: Defined as blood loss of > 1000 cc of blood after delivery prior to six-week visit.
 
Analysis population: Safety

Maternal mortality through 42 days	Binary	
The unit of analysis will be women randomized. Per the protocol, maternal mortality is defined as: "the death of a woman during pregnancy (i.e. conception to delivery) and the puerperium (i.e. up to 42 days after delivery)." The event will be defined as "Yes" if the woman dies prior to 42 days after delivery and "No" otherwise. This outcome measure will be obtained from forms MN02 and MN03 in the MNH Registry. If the 42-day outcome is missing and the woman was alive at the last known follow-up, this outcome will be treated as missing.
 
Analysis population: ITT

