Hypertensive Disorders, N (%)				
GN01: DRC				
GN03: Zambia				
GN12: Kenya				
GN06: Guatemala				
GN08: Belagavi				
GN11: Nagpur				
GN09: Pakistan				
Small for Gestational Age				
GN01: DRC				
GN03: Zambia				
GN12: Kenya				
GN06: Guatemala				
GN08: Belagavi				
GN11: Nagpur				

Outcome Measure	Risk of Outcome			
	Placebo N = XXXX	Aspirin N = XXXX	RR (95% CI)	p-Value
GN09: Pakistan				
Perinatal Mortality				
GN01: DRC				
GN03: Zambia				
GN12: Kenya				
GN06: Guatemala				
GN08: Belagavi				
GN11: Nagpur				
GN09: Pakistan				
Preeclampsia				
GN01: DRC				
GN03: Zambia				
GN12: Kenya				
GN06: Guatemala				
GN08: Belagavi				
GN11: Nagpur				
GN09: Pakistan				
Eclampsia				
GN01: DRC				
GN03: Zambia				
GN12: Kenya				
GN06: Guatemala				
GN08: Belagavi				
GN11: Nagpur				
GN09: Pakistan				

*NOTE: Table contains outcomes summarize using MITT population as well as outcomes summarized using ITT population. Final table will clearly identify which population is used for each outcome. Birth weight will be summarized both including and excluding estimated weights. Footnotes will be included to describe p-value and RR is from unadjusted model that includes a site by treatment group interaction term. The p-value for the interaction term will also be presented.*

Table 6: Serious Adverse Event Summary

Variable	Placebo N (%)	Aspirin N (%)	Relative Risk RR (95% CI)	p-Value
Randomized, N				
Participants with at least one SAE 				
Maternal death  , N (%)				
Fetal loss after 20 weeks  , N (%)				
Fetal anomaly  , N (%)				
Antepartum hemorrhage  , N (%)				
Post-partum hemorrhage  , N (%)				
Preeclampsia/Eclampsia  , N (%)				
Upper GI bleeding  , N (%)				
Gastroschisis, N (%)				
At least one Other SAE  , N (%)				

The denominator for this table is any woman included in the safety population.

Table 7a: Summary of Protocol Deviations by Treatment Arm

Variable	Arm 1	Arm 2	Total
Randomized, N (%)	XXXX	XXXX	XXXX
At least one protocol deviation, N (%)	XXX (Y.Y)	XXX (Y.Y)	XXX (Y.Y)
Protocol deviations, N	XX	XX	XX
Study participant enrolled but did not meet inclusion criteria	XX	XX	XX
Study participant enrolled but met criteria requiring exclusion	XX	XX	XX
Study participant enrolled twice	XX	XX	XX
Medication card was lost or destroyed	XX	XX	XX
The study participant was incorrectly randomized	XX	XX	XX

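### Maternal death, postpartum haemorrhage and antepartum haemorrhage are scored from registry forms alone, although each also triggers an SAE form and no rule reconciles the two sources.

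*Combined protocol and SAP*

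**What the plan says.** **Outcome definitions (SAP 9.2).** Postpartum haemorrhage: "This outcome will be defined based on Question A8c from Form MN02 or Question B7 from Form MN03 from the MNH Registry". Maternal mortality through 42 days: "This outcome measure will be obtained from forms MN02 and MN03 in the MNH Registry". The missing-data rule for death is: "If the 42-day outcome is missing and the woman was alive at the last known follow-up, this outcome will be treated as missing". Antepartum haemorrhage comes from registry item A8b on Form MN02. None of the three definitions mentions the SAE form.

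**SAE collection (Protocol 3.5.1).** "The specific adverse events to be monitored in this trial include maternal death, upper GI bleeding (vomiting blood), fetal anomaly, gastroschisis, post-partum hemorrhage", and the list ends with antepartum haemorrhage. The section continues: "The occurrence of any of these events will also trigger completion of the Serious Adverse Events Form". No blood-loss threshold is attached to either haemorrhage. Protocol 3.5.2 adds that maternal deaths go to the data coordinating center within 48 hours of the senior investigator's notification.

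**A different rule elsewhere in SAP 9.2.** For hypertensive disorders of pregnancy, the first item that counts as evidence is "Any reported SAE of preeclampsia or eclampsia", alongside a registry report or qualifying blood pressures.

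**Reporting (SAP 14).** Table 5a lists all three harms with relative risk and p-value. Table 6, the SAE summary, lists all three again with relative risk and p-value, and notes: "The denominator for this table is any woman included in the safety population".

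**Masked review (SAP 7.6).** The stated questions are the per-protocol population, the primary outcome and selected secondary outcomes. The three harms here are classed as other outcomes of interest.

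**The concern.** The trial collects these events by two routes but defines the outcome from one. An SAE form reporting a haemorrhage or death has no stated path into the Table 5a variable if the registry form is absent or silent. The report will then carry two estimates for each harm, and the plan does not say how a difference is to be explained or which one supports the safety conclusion. That choice would fall after unmasking.

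Protocol 2.8 says earlier studies did not assess aspirin in pregnancy in the developing world, where anaemia may be endemic, and makes safety monitoring a strong focus. It names antepartum and postpartum haemorrhage, and maternal death due to postpartum haemorrhage, for ongoing monitoring. SAP 10 plans no formal safety analysis, so these tables carry much of the evidence on maternal harm.

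**Working it through.** The plan states no event rate, capture rate or power for these harms, so there is no figure to reproduce. The check is mainly a comparison of text.

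**1. Sources and populations side by side**

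| Harm | Table 5a source | Table 5a population | SAE form required? | Table 6 population |
|---|---|---|---|---|
| Maternal death | MN02, MN03 | ITT | Yes | Safety |
| Postpartum haemorrhage | MN02 A8c or MN03 B7 | Safety | Yes | Safety |
| Antepartum haemorrhage | MN02 A8b | mITT, delivery after 22 weeks | Yes | Safety |
| Hypertensive disorders, for contrast | SAE, registry or blood pressures | mITT | Counted in the outcome | Safety (preeclampsia/eclampsia row) |

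For postpartum haemorrhage the population is the same in both tables, so a difference could come only from source or definition. For the other two harms the population can also move the figures.

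**2. Definitions**

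The protocol counts a postpartum loss of at least 1000 ml; the registry manual, as cited in SAP 9.2, requires more than 1000 cc. A recorded loss of exactly 1000 ml meets the first and not the second. For antepartum haemorrhage the protocol gives no volume, while the registry manual requires more than 1000 cc. The SAE trigger gives no volume for either.

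**3. Applying the rules to two records**

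- *SAE form reports postpartum haemorrhage; registry items A8c and B7 are not 'Yes'.* The outcome is defined from A8c or B7, so the SAE report does not enter. SAP 9.2 writes no explicit Yes/No/missing rule here, so whether she becomes 'No' or missing is not stated.
- *SAE form reports a death within 42 days; the registry has no 42-day form.* The general rule is 'Yes' if she dies, but the source is limited to MN02 and MN03. The missing rule turns on her being alive at last known follow-up, and the text does not say whether SAE data count there. The coding is ambiguous.

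**4. Possible size for maternal death (assumed rates)**

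Expected deaths per arm = 5,960 × rate.

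- 100 per 100,000: 5,960 × 0.001 = 6.0; one missed death is 1/6.0 = 17% of the arm's deaths.
- 300 per 100,000: 5,960 × 0.003 = 17.9; one missed death is 1/17.9 = 6%.

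**5. Possible size for postpartum haemorrhage (assumed rates)**

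Assume 5,900 per arm, true placebo risk 2%, true relative risk 1.5, and that each source independently captures a fraction *s* of cases. Observed risk from one source is risk × *s*; from either source it is risk × [1 − (1 − *s*)²]. Power for two proportions, two-sided 0.05, is

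Φ{[|p₁ − p₀|√n − 1.96√(2p̄(1 − p̄))] / √[p₀(1 − p₀) + p₁(1 − p₁)]}.

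For *s* = 0.6: one source gives p₀ = 0.012 and p₁ = 0.018, power 0.765; either source captures 1 − 0.4² = 0.84, power 0.889.

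| *s* | One source | Either source |
|---|---|---|
| 0.60 | 0.765 | 0.889 |
| 0.80 | 0.874 | 0.926 |
| 0.90 | 0.909 | 0.933 |
| 0.95 | 0.924 | 0.935 |

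If the sources overlap fully, the gain is zero.

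**6. Effect of SAE reports below the outcome threshold**

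If merging also adds sub-threshold reports in 1% of each arm (assumption), the either-source risks at *s* = 0.6 are 0.02 × 0.84 + 0.01 = 0.0268 and 0.03 × 0.84 + 0.01 = 0.0352. The relative risk falls to 1.31 and power to 0.749, below the 0.765 from one source. At *s* = 0.8 the relative risk is 1.33 and power 0.821, against 0.874 from one source. With only 0.25% added, the combined rule still gains: 0.854 at *s* = 0.6 and 0.901 at *s* = 0.8. Automatic merging of haemorrhage reports is therefore not a safe improvement. Death needs no volume threshold, so this difficulty does not arise for it.

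**The case against.** The registry is the protocol's designated source: Protocol 4 says maternal and fetal outcomes are documented through it. An outcome table next to an SAE table is a normal layout, SAE-form events still appear in Table 6, and SAEs go to the DMC. SAP 7.3 expects 2% or less missing on maternal morbidity and mortality measures. SAE forms draw on medical records and patient reports at the same sites, so the sources may overlap heavily. SAP 7.5 makes safety p-values descriptive, so power is a weak yardstick. SAP 7.6 does not say that its list of questions is exhaustive.

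Most of this stands, and it limits the point. A reader might infer that the trial will publish conflicting risks; the text supports only that it can, if the sources disagree or the populations differ. A reader might infer that an SAE-only haemorrhage is scored 'No', or that an SAE-known death is coded missing; neither is written. A reader might infer that known events vanish from the report; they do not, since Table 6 shows them. Large power gains follow only from low, independent capture with no false positives, which nothing in the documents supports.

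What does not fall away is the missing rule. Naming the registry as the source does not settle a disagreement with an SAE form, low missingness does not establish that the registry captures every event, and the hypertensive-disorder definition shows that using both sources is within the SAP's own practice.

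**Conclusion.** The concern holds as a gap in the outcome definitions. For maternal death, postpartum haemorrhage and antepartum haemorrhage, SAP 9.2 names only registry forms, the protocol requires an SAE form for each, and nothing reconciles the two. An event known only from an SAE form can be left out of Table 5a, and Tables 5a and 6 can show different relative risks for the same harm.

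The size is unknown. The illustrations above rest on assumed event and capture rates: one missed death is 6% to 17% of an arm's deaths, and the power gain for postpartum haemorrhage runs from nil to about 12 points, or turns negative if many sub-threshold SAE reports are merged. If sources agree, the gap has no effect. The primary test of preterm birth and participant monitoring by the DMC are not affected. The case is clearest for death.

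**What to change.** - **Maternal mortality (SAP 9.2):** score 'Yes' if MN02, MN03 or an SAE form reports death during pregnancy or up to 42 days after delivery. Score 'missing' only when no source gives 42-day status.
- **Postpartum and antepartum haemorrhage:** list registry-SAE disagreements without treatment arm. Extend the SAP 7.6 masked review to resolve them before lock against one stated outcome definition for each. The differing blood-loss wording in the protocol and the registry manual must be reconciled first. Use the resolved variable in Table 5a. Do not merge SAE-only reports automatically.
- **Table 6:** keep it as a count of SAE reports, so that it stays consistent with its row for participants with at least one SAE. Add a footnote explaining any difference from Table 5a, including ITT or mITT against Safety.

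Cost: SAP wording, one merge of data already held, and a short list for a review already planned. SAE reporting may vary between sites. Stratifying the test by site does not correct misclassified outcomes, so the disagreement list should be shown by site.
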